### 9.2 **Population Demographics**

The demographics and medical history will be presented in tabular form for all subjects enrolled in this study (ITT analysis set). Means, standard deviations, and sample size will be used to summarise continuous characteristics such as age. Frequencies and percentages will be used to summarise categorical characteristics such as gender. Demographic and medical history data will be additionally tabulated for the mITT and PP analysis sets.

### 9.3 Primary Endpoint Analysis

Endpoints will be analysed using the modified intention-to-treat analysis set. An additional supportive analysis will be conducted in the ITT and PP analysis sets for the primary safety and effectiveness endpoints. All available data will be used for each endpoint and no imputations will be done.

The primary safety endpoint of MAE at 30 days will be presented as frequency and percentage and the 2-sided 95% confidence interval will be calculated via Agresti-Coull.

Similarly, the primary outcome measure for effectiveness, clinically-driven target lesion revascularisation (TLR) through 12 months, will be presented as frequency and percentage and the 2-sided 95% confidence interval will be calculated via Agresti-Coull.

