### 4.1.2 **Primary effectiveness endpoint:**

The primary outcome measure for effectiveness will be freedom from clinically-driven target lesion revascularization (CDTLR) through 12 months.

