### 5.4 Withdrawal

Patients may withdraw at any time from the Study without prejudice; participation is entirely voluntary. If a subject prematurely terminates from the Study, the reason for termination will be recorded in the eCRF.

The Investigator should follow all unresolved serious adverse events until the events are resolved, the subject is lost to follow-up, the subject has withdrawn consent, the subject completes the Study follow-up, or the adverse event is otherwise explained.

All reasonable efforts will be made to obtain complete data for all subjects; however, missing observations will occur due to loss to follow-up, withdrawal, or variation in site standard of care assessments. Site shall make all reasonable efforts to contact subjects who do not respond to follow-up requests. In the event patient does not respond to a final contact attempt via certified letter, patient will be considered lost to follow-up. Patients who withdraw consent after treatment will have their data evaluated until the time of their withdrawal (unless consent for data retention is removed in accordance with local or national regulations). Patients who withdraw or are lost to follow-up will not be replaced.

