### 9.0 STATISTICAL ANALYSIS PLAN

The analysis of the data from this study will be primarily descriptive. Continuous endpoints will be summarized by N, mean, standard deviation, median, minimum, and maximum. Categorical or binary endpoints will be summarised by N and percentage with confidence intervals as appropriate. Kaplan Meier plots will be used to display and summarise time to event data.

The planned sample size for analysis is at least 500 patients which is believed to be adequate to provide an accurate characterisation of BioMimics 3D in a "real-world" clinical settings.

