#### 9.6 Sample Size

This study is not powered for formal statistical hypothesis testing and is intended to be descriptive in nature. Assuming an MAE rate of 90% to 99%, the corresponding width of the 95% confidence interval would range from 5.5% to 2%, respectively. Similarly, assuming an event rate of 75% for CDTLR at 12 months, the width of the 95% confidence interval would be approximately 8% allowing for up to 10% attrition. Thus, it is felt that enrolling 500 subjects provides adequate precision to estimate the primary endpoint event rates in this cohort.

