### 9.7 Handling of Missing Data

No imputation of missing data is planned. Subjects who have ascertainment of status at a later out-ofwindow date (for example, subjects who are known to be free of MAE past 30 days but missed the 30 day visit) are not considered missing as their status is known and their data will be used.

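### The 12-month CDTLR endpoint is planned as a crude percentage whose implied denominator drops event-free partial follow-up; naming a Kaplan-Meier estimate in section 9.3 would avoid a modest bias

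*Combined protocol and SAP*

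**What the plan says.** Section 4.1.2 defines the primary effectiveness endpoint as "freedom from clinically-driven target lesion revascularization (CDTLR) through 12 months". Section 9.3 analyses its complement on the mITT set: "clinically-driven target lesion revascularisation (TLR) through 12 months, will be presented as frequency and percentage and the 2-sided 95% confidence interval", the interval being Agresti-Coull.

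Four other statements bear on patients who leave early:

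- Section 9.3: "All available data will be used for each endpoint and no imputations will be done".
- Section 9.7 repeats that nothing is imputed. It adds that subjects whose status is learned at a later, out-of-window date "are not considered missing as their status is known and their data will be used".
- Section 9.6: "the width of the 95% confidence interval would be approximately 8% allowing for up to 10% attrition".
- Section 5.4: "Patients who withdraw or are lost to follow-up will not be replaced". The same section says that data from patients who withdraw consent are evaluated up to withdrawal.

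Section 9.0 contains the only mention of the survival method: "Kaplan Meier plots will be used to display and summarise time to event data". It names no endpoint, time point or interval, and neither 9.3 nor 9.4 refers back to it.

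**The concern.** An endpoint that runs through 12 months, with some patients leaving before then, is a time-to-event outcome with censoring. A crude percentage needs a rule for patients lost without an event, and the plan gives none explicitly. The rule it implies is to count only patients with known status.

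That rule treats the two kinds of lost patient differently. Someone who has a CDTLR in month 4 and leaves in month 6 counts as an event. Someone who leaves in month 6 without a CDTLR is removed, although six months of event-free observation exist. Events are kept and event-free time is dropped, so the rate tends to be too high and freedom from CDTLR too low.

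The study is descriptive. Section 9.6 justifies its size by the precision of the primary event rates, so what is at stake is the accuracy of one headline rate and its interval.

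**Working it through.** **Inputs.** 500 patients (3.3, 9.6), up to 10% attrition (9.6), and the 9.6 assumption, worded as "assuming an event rate of 75% for CDTLR at 12 months". I read the 75% as freedom from CDTLR, that is 25% events. The interval width is the same under either reading. My own assumptions are exponential event and loss times and loss independent of outcome.

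**1. Reproduce the plan's width.** With n = 500 × 0.90 = 450 and p = 0.75:

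- Wald: 2 × 1.96 × √(0.75 × 0.25 / 450) = 8.00 points.
- Agresti-Coull: 7.99 points (70.8% to 78.8%).
- Agresti-Coull with n = 500: 7.58 points.

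The figure of about 8% is correct, and n = 450 matches it best. Because 7.58 also rounds to 8, the number alone does not prove which n was used. The attrition wording, however, shows that lost patients were taken out of the denominator.

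**2. Expected crude rate when loss is spread over the year.** Let λ = −ln 0.75 = 0.2877, δ = −ln 0.90 = 0.1054, and follow-up be 1 year.

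- Event observed: λ/(λ+δ) × (1 − e^−(λ+δ)) = 0.7319 × 0.325 = 0.2379, or 118.9 patients.
- Lost event-free: 0.2681 × 0.325 = 0.0871, or 43.6 patients.
- Followed event-free: 0.675, or 337.5 patients.
- Known-status rate: 0.2379 / (1 − 0.0871) = 26.1%, against a true 25.0%.

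**3. Same calculation, other conditions.**

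- All loss at day 30: of 50 patients leaving, 1.2 have had an event and 48.8 have not. The rate is (112.5 + 1.2) / (500 − 48.8) = 25.2%.
- 5% loss over the year: 0.2440 / (1 − 0.0435) = 25.5%.
- 10% events with 10% loss: 0.095 / 0.905 = 10.5%, against a true 10.0%.

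**4. Coverage of the 95% interval.** Simulated with N = 500 and 25% true events, 20,000 trials (8,000 for the rows with a visit window). Monte Carlo standard error is about √(0.92 × 0.08 / 20,000) = 0.2 points.

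| Condition | Estimator | Mean CDTLR | Coverage |
|---|---|---|---|
| 10% loss over the year, others followed to day 365 | Crude, known status | 26.1% | 91.6% |
| Same loss, visits uniform on 365 ± 30 days | Crude, known status | 25.6% | 93.9% |
| Same loss, visits uniform on 365 ± 60 days | Crude, known status | 25.2% | 94.6% |
| 5% loss over the year | Crude, known status | 25.5% | 94.2% |
| 10% loss, all at day 30 | Crude, known status | 25.2% | 94.6% |
| 10% loss over the year, true loss dates | Kaplan-Meier, log-log | 25.0% | 95.0% |
| Same loss, visits on ± 30 or ± 60 days | Kaplan-Meier, log-log | 25.0% | 94.9% to 95.0% |
| Same loss, event-free losses dated back to discharge or day 30 | Kaplan-Meier, log-log | 25.9% | 92.2% |
| Same loss, losses dated to a declaration after month 12 | Kaplan-Meier, log-log | 23.8% | 91.6% |

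In the visit-window rows a second error partly offsets the first. Roughly half of the retained event-free patients are seen before day 365 and are counted as event-free at 12 months, which pulls the crude rate back down.

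The Kaplan-Meier interval with true loss dates has a mean width of 7.8 points (7.9 to 8.1 with the visit window), so the precision stated in 9.6 is kept.

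**The case against.** Much of the case on the other side stands.

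- **The handling of losses is not wholly open.** A reader might infer that the denominator could equally be all mITT patients, which would give 23.8% and a 2.3-point gap between the two crude readings. The documents do not support that. No imputation, known-status patients being the ones not treated as missing, and a width that fits n = 450 all point the same way. The rule is implied; what is lacking is a sentence saying so.
- **Kaplan-Meier is not absent.** Section 9.0 promises it for time-to-event data, and this endpoint is an obvious candidate. But 9.3 names a different estimate and interval for this endpoint, so the general sentence does not replace it.
- **The 1-point bias with 92% coverage is an upper-end case.** It needs 25% events, the full 10% loss, and every retained patient followed to day 365. Section 9.7 also recovers patients whose status is learned later, and telephone contact is allowed, so true loss at month 12 may be smaller.
- **A much worse figure can be constructed.** If all loss fell just before month 12, the crude rate would be 125 / 462.5 = 27.0% with coverage near 82%. Nothing in the documents suggests that pattern.
- **The promise in 5.4 does not settle the matter.** Evaluating data until withdrawal is satisfied by counting events before withdrawal. It does not commit the plan to a censored analysis.
- **Kaplan-Meier is also a choice of estimand.** Censoring deaths gives 25.0%, whereas cumulative incidence with death as a competing event gives 24.6% at an assumed 3% mortality and 24.4% at 5%. That difference is of the same order as the crude bias in several rows above.

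What remains is that the named estimator discards usable follow-up, and a standard method would not.

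**Conclusion.** The point holds, at minor to moderate weight. The crude percentage in 9.3, on its implied known-status denominator, tends to overstate the CDTLR rate by about 0 to 1 point. Coverage ranges from about 92% to near nominal, depending on when patients are lost and how 12-month visits are spread.

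These sizes assume 25% events and non-informative loss of at most 10%. The visit-window results also assume uniform visit dates and rest on partly cancelling errors. If loss is related to outcome, neither the direction nor the size is determined here, and Kaplan-Meier would not be protected either.

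The 8% width in 9.6 is not in error. The study tests no hypothesis and no decision turns on this rate, so a reader should not infer that its conclusions are at risk.

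**What to change.** In section 9.3:

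- Name the Kaplan-Meier estimate of freedom from CDTLR at day 365, with a log-log Greenwood 95% interval, as the primary effectiveness estimate.
- Censor at withdrawal or at the last documented contact of any kind at which event-free status is known. Do not censor at the date a patient is declared lost.
- State how event-free contacts inside the 12-month window but before day 365 are treated. First reconcile the window, which is ±60 days in 3.4 and ±30 days in 6.1, Table 1 and 6.4.
- Keep the Agresti-Coull percentage as supportive, with its denominator and the number lost event-free shown.
- Optionally, add cumulative incidence with death as a competing event as a sensitivity analysis.

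The cost is SAP wording and a little more analysis, with no extra patients or visits. The condition is a last-contact date in the eCRF. Section 5.4 mentions recording the reason for termination but not the date, so this should be confirmed. No contact is scheduled between day 30 and month 12. If losses can be dated only to discharge or day 30, Kaplan-Meier removes little of the bias (25.9% against 26.1% for the crude rate), and 95% coverage should not be claimed.

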### 9.4 Secondary Endpoint Analysis

All secondary endpoints will be tabulated. Means, standard deviations and sample size will be used to summarise continuous characteristics. Distributions of continuous data will be examined and if nonnormality is exhibited, medians and interquartile ranges will be presented. Frequencies and percentages will be used to summarise categorical characteristics. Measures collected serially over time (for example, Rutherford Clinical Category) will be presented at each time point, and the measure at each time point will be compared to the baseline measure as well as tested for trends. All available data will be used for each endpoint and no imputations will be done. The mITT analysis set will be used for these analyses. As a secondary analysis, the PP analysis set will be displayed.

### 9.5 Site Poolability

Poolability of study subjects across investigational sites will be explored by comparing the primary outcome measure across site. Testing of the primary outcomes will be conducted across site at a two-sided alpha=0.15 level using a chi-square test, unadjusted for covariates. If differences between sites exist at the alpha=0.15 level, summary statistics will be presented for each site. Any differences by study site will be discussed in the study report. If substantial differences emerge, a sensitivity analysis of the primary outcomes may be performed by excluding outlying sites from the analysis.

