#### 3.3 Enrolment

A minimum of 500 patients will be enrolled in the study. The study will be conducted at up to 40 centres in any country where CE Mark is recognised and the device is legally marketed.

A minimum of 50 patients treated with drug coated balloon (DCB) will be enrolled (DCB cohort). All primary and secondary endpoints will be assessed separately for this cohort.

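### Section 9.5 requires per-site results only if a low-powered chi-square test gives p < 0.15; they should be shown whatever the p-value

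*Combined protocol and SAP*

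**What the plan says.** Section 9.5 (Site Poolability) introduces the check as exploratory: "Poolability of study subjects across investigational sites will be explored by comparing the primary outcome measure across site". The method is fixed: "Testing of the primary outcomes will be conducted across site at a two-sided alpha=0.15 level using a chi-square test, unadjusted for covariates". One sentence ties site tables to the result: "If differences between sites exist at the alpha=0.15 level, summary statistics will be presented for each site".

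Two further sentences follow. The first carries no significance condition: "Any differences by study site will be discussed in the study report". The second is optional and opens with an undefined condition, "If substantial differences emerge", after which "a sensitivity analysis of the primary outcomes may be performed by excluding outlying sites from the analysis". The plan does not say what makes a difference substantial or a site outlying. It gives no minimum site size, no rule for grouping small sites, and no estimate of between-site variation.

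On scale, Section 3.3 (Enrolment) sets a minimum of 500 patients and says: "The study will be conducted at up to 40 centres in any country where CE Mark is recognised and the device is legally marketed". Section 9.6 states that the study is not powered for hypothesis tests. Section 9.3 plans one overall estimate per primary endpoint in the mITT set, whatever the site test shows.

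**The concern.** The only stated requirement to tabulate results by site rests on a hypothesis test with up to 39 degrees of freedom and very few events per site, in a study that declares itself unpowered for testing. If p is 0.15 or more, the plan requires no site table and no measure of spread. The discussion of site differences that it does promise comes with no table, interval or estimate.

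Section 1.7 gives the purpose as understanding performance in real-world use with a wider range of operators, so variation between sites bears on the objective. A cluster of sites with a clearly higher event rate could go untabulated. A reader of the report could also take a non-significant result under the heading of poolability as reassurance that the test cannot give.

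**Working it through.** **1. Inputs.** At least 500 patients and up to 40 sites (Section 3.3). Level 0.15 (Section 9.5). Planning rates of 90% to 99% for MAE and 75% for CDTLR, with up to 10% attrition (Section 9.6). I read those rates as event-free, that is 1% to 10% MAE events and 25% CDTLR events. The spread between sites, the number of high-rate sites, the 3% MAE rate (inside the 1% to 10% range) and the 10% CDTLR rate (not in the documents) are assumptions.

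**2. The plan's own figures.** No power is stated for the site test, so the confidence interval widths in Section 9.6 are the figures to reproduce. With n = 500 × 0.9 = 450 and Wald width 2 × 1.96 × √(p(1−p)/n):
- 90%: 5.54 points (stated 5.5%).
- 99%: 1.84 points, or 2.17 by Agresti-Coull (stated 2%).
- 75%: 8.00 points (stated about 8%).

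These agree to rounding, so the inputs are read as the plan intended.

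**3. Information per site.** 500/40 = 12.5 patients, and 450/40 = 11.25 at 12 months. Expected events per site:
- MAE 1%: 0.125. MAE 10%: 1.25.
- CDTLR 10%: 1.125. CDTLR 25%: 2.81.

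All are below the usual minimum of 5 for the chi-square approximation. With the tabulated critical value, the simulated false-trigger rate is 0.12 to 0.14 for 40 equal sites, and up to 0.23 with unequal sites at MAE 1%.

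**4. Miss rates, a group of high-rate sites.** Pearson chi-square across 40 near-equal sites, with the critical value set by simulation so that the 0.15 level holds. A miss is a result at or below that value.

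| Scenario (40 sites) | Missed |
|---|---|
| MAE 3%, four sites tripled | about 71% |
| MAE 3%, ten sites doubled | about 77–78% |
| MAE 10%, ten sites doubled | about 56% |
| CDTLR 10%, ten sites doubled | about 59% |
| CDTLR 25%, four sites doubled | about 43% |
| CDTLR 25%, ten sites doubled | about 13% |

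The choice of critical value changes little. With the tabulated value, the first row becomes 73%. With 20 sites and the same share of high-rate sites, the two MAE 3% rows fall only to about 64% and 73%, while the last row falls to about 5%.

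**5. Cross-check, smooth variation.** Site rates drawn from a logit-normal distribution with SD 0.5, 40 equal sites, tabulated critical value. For scale, this puts 90% of sites between about 2% and 11% around a typical 5%, or between 13% and 43% around 25%. Miss rate = 1 − trigger probability:
- MAE 1%: 85%. MAE 5%: 68%. MAE 10%: 51%.
- CDTLR 10%: 54%. CDTLR 25%: 26% (about 15% with 20 sites).

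Over logit SDs from 0.3 to 1.0, the trigger probability with 40 equal sites runs from 12% (MAE 1%) to nearly 100% (CDTLR 25%).

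**6. What a non-significant result leaves open.** Take chi-square = 39 on 39 df, an unremarkable value, at CDTLR 25%. Dividing by the 2.5th percentile gives 39/23.65 = 1.65. Setting 1 + (11.25 − 1) × ICC = 1.65 gives ICC = 0.65/10.25 = 0.063. The between-site SD is then √(0.063 × 0.25 × 0.75) = 0.109. So this result is compatible, on a rough calculation, with a between-site SD of up to about 11 percentage points.

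**The case against.** The strongest reply is that nothing important hangs on the test. The section speaks of exploring poolability and sets no rule to pool or not to pool; Section 9.3 reports the overall estimate regardless. The study is single-arm and descriptive, so no primary estimate or interval changes. This stands, and it limits the weight of the point.

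A reader might infer that the plan takes p ≥ 0.15 as evidence that sites are alike. It does not say so. A reader might also infer that site results are withheld after a non-significant test. The text states a trigger for presenting them, forbids nothing, and promises without any significance condition that site differences will be discussed. What remains is that no site table or estimate is then required.

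The level of 0.15 is already a concession to low power. That is fair, but the miss rates above include it. Forty is also an upper limit on sites; 20 sites help a good deal for CDTLR at 25% and little for MAE at 3%.

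Lastly, per-site rates from about 12 patients are mostly noise, and a between-site SD will have a wide interval. This too is correct. By the method of step 6, MAE 3% with 500 patients gives ICC = 0.65/11.5 = 0.057 and an upper SD of √(0.057 × 0.03 × 0.97), about 4 points, which exceeds the rate itself. An upper bound used as a pass/fail criterion would therefore seldom be met even by homogeneous sites. The SD should be reported as an estimate, with no verdict attached.

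**Conclusion.** The point holds as one about reporting. The trigger for per-site summaries has low power for 30-day MAE (about 71% to 78% missed at 3% with 40 sites, and still about 64% to 73% with 20) and for modest or few-site differences in CDTLR (about 59% missed at 10% with ten sites doubled). It works reasonably for large differences at the plan's own CDTLR rate: about 13% missed with ten of 40 sites doubled, though 43% with four.

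A general claim that the test misses relevant differences in most studies is not supported. The documents give neither a site spread nor a size of difference that matters, and the result changes with both. The figures rest on assumed site effects, near-equal site sizes, and the reading of the planning rates as event-free. A non-significant result cannot be read as evidence of homogeneity. The change is a worthwhile, cheap improvement and does not correct any primary estimate.

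**What to change.** In Section 9.5, for both primary outcomes:
- Present coded per-site results with intervals, for example a funnel plot with a table, regardless of the p-value.
- Report the between-site SD with its 95% CI from a random-intercept logistic model, as a descriptive estimate and not as a pass/fail test of homogeneity.
- Keep the chi-square p-value as descriptive only, and state that p ≥ 0.15 is not evidence that sites are alike.
- Where events are too few (MAE near 1%), state that between-site variation could not be assessed.

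Cost: a few sentences in the plan, one table or plot and one model per primary outcome, and no new data. The downside is noisy per-site rates, which is why they need intervals, and a report that may have to leave the question of site variation open.
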